### **Secondary End-Points Aim 1:**

**Aim 1a.** We will test whether cardiac risks factors (blood pressure, age, sex, glucose or cholesterol levels, prior history of cardiac disease, LVEF at baseline) or cancer specific risk factors (anthracycline dose, radiotherapy) are predictive of the effect of statins on LVEF.

***Analysis Plan:*** In patients treated with statins, we will use a logistic regression model to evaluate whether cardiac risks factors or cancer specific risk factors are predictive of the effect of statins on LVEF. Patients on statins and eligible for statins will be excluded. Therefore, cholesterol levels will be relatively homogenous, and we will not pre-stratify our cohort based on cholesterol. Radiotherapy is not routinely used in the cohort and is used in <5% of cases, there we will also not pre-stratify based on the use of radiotherapy. However, we will use cholesterol values (as a continuous variable) and the use of radiotherapy (as a binary variable) to perform a post-hoc analysis. Additionally, all patients are intended to have the same dose of anthracyclines and dose adjustments are made during therapy in response primarily to toxicities. Therefore, we will additionally test the interaction between the dose of anthracyclines and the effect of statins as a post-hoc analysis.

**Aim 1b.** We will test whether statins reduce cardiac events. The study is not powered to test the effect of atorvastatin on clinical events.

***Adjudication plan:*** The occurrence of clinical adverse cardiac events will be adjudicated based on consensus opinion of a clinical adjudication committee containing three board-certified cardiologists blinded to experimental group (Drs. [name], [name] and [name]).

***Analysis Plan:*** All statistical analyses will be performed based on intent-to-treat. Fisher exact tests will be used to determine whether statins decrease the combined end-point of death or heart failure.

**Aim 1c.** We will test whether statins are safe.

***Analysis Plan:*** Chi-square will be used to test for differences between the two treatment groups for categorical secondary endpoints.

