## b. Previous studies supporting the proposed research

*Evidence to support the primary hypothesis that statins will prevent the anthracycline-induced reduction in LVEF:* We prospectively recruited 72 patients with breast cancer undergoing anthracycline-based chemotherapy and measured LVEF prior to and after 12 months. In total, 8 patients (11%) were treated with statins prior to the initiation of chemotherapy. There was no

difference in the baseline LVEF between patients who were or were not on statins prior to chemotherapy ( $64\pm 5\%$  in both groups). After anthracyclines, there was no decrease in LVEF in the statin group ( $64\pm 9\%$ ); in comparison there was a decrease of 5% in the LVEF in the placebo groups ( $59\pm 6\%$ ,  $p=0.06$ ). This trend persisted even after adjustment for traditional cardiovascular risk factors and for treatment by ACE inhibitors and beta-blockers ( $p=0.08$ ). Similarly, in a retrospective study, Chotenimitkhun *et al.* tested the effect of incidental statin therapy on the reduction in LVEF after anthracyclines among 52 patients. They found that the LVEF after anthracyclines was unchanged in the statin group but the LVEF was 7% lower in the placebo-treated group. In the only randomized clinical trial testing the effect of statins on LVEF, Acar *et al.* found that the LVEF was unchanged among the 20 patients in the statin-treated group and was decreased by 9% among the 20 patients on placebo. **Therefore, preliminary data support the hypothesis that there is no decrease in LVEF after anthracyclines among patients on statins.**

*The rate of death or heart failure admission after treatment with anthracyclines is higher among patients with lymphoma than in other patients treated with anthracyclines:* Overall, 1644 consecutive MGH patients with lymphoma treated with anthracyclines were followed for a median of 3 years. In that period, 67 (4%) developed symptomatic heart failure or cardiac death. In comparison, the other major population that is treated with anthracyclines are patients with breast cancer. In a similar follow-up period of 3 years, 5 (0.7%) of 711 patients with breast cancer developed symptomatic heart failure or cardiac death ( $P<0.0001$  vs. lymphomas).

**Therefore, patients with lymphomas have a higher rate of cardiac death or heart failure from anthracyclines than other similarly-treated cancer populations.**

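### Aim 1a asks which factors change the statin effect, but its model uses statin patients only and so cannot answer that question

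*SAP*

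**What the plan says.** The question in Aim 1a (SAP, Secondary End-Points Aim 1; Protocol 13.1) is about effect modification. It asks whether listed factors "are predictive of the effect of statins on LVEF". Seven are cardiac: blood pressure, age, sex, glucose, cholesterol, history of cardiac disease and baseline LVEF. Two relate to the cancer: anthracycline dose and radiotherapy.

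The analysis plan then names one model: "In patients treated with statins, we will use a logistic regression model to evaluate whether cardiac risks factors" or cancer factors predict that effect. Patients already on statins, or eligible for them, are excluded from the trial, so the model population can only be the atorvastatin arm.

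Three of the nine factors receive something further:

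- Anthracycline dose: "we will additionally test the interaction between the dose of anthracyclines and the effect of statins as a post-hoc analysis".
- Cholesterol and radiotherapy: "we will use cholesterol values (as a continuous variable) and the use of radiotherapy (as a binary variable) to perform a post-hoc analysis". The plan gives no model, population or interaction term for these.

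The other six factors receive only the statin-arm model. The dependent variable is not named. A logistic model implies a binary outcome, taken here to be AIC, the primary endpoint.

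**The concern.** Within one arm treatment does not vary, so no coefficient can measure how the treatment effect differs between patients. The model estimates prognosis on statin. Two wrong conclusions can follow:

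- A factor that raises AIC risk by the same odds ratio in both arms can be reported as changing the statin effect when, on the odds-ratio scale, it does not.
- A factor that does change the effect, but is unrelated to AIC among statin patients, is missed.

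The first could lead to a report that statins protect less well in a group that is simply at higher risk in either arm. The second could hide the group that gains most.

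**Working it through.** **Inputs.** SAP, Primary End-Point: AIC in 20% on placebo and 5% on statin; 270 evaluable patients; two-sided 0.05. Protocol 1.0: 1:1 allocation, hence 135 per arm. The documents give no factor strengths, so these are assumptions shown as a range.

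**The plan's own figure.** Aim 1a has none. The primary power confirms the rates and arm sizes: [0.15 − 1.96 × √(2 × 0.125 × 0.875/135)] / √[(0.20 × 0.80 + 0.05 × 0.95)/135] = (0.15 − 0.0789)/0.0392 = 1.81, giving 96.5%. This agrees with the SAP's statement of more than 90%.

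**Events.** Statin 135 × 0.05 = 6.75; placebo 135 × 0.20 = 27; both arms 33.75. If all nine factors entered one statin-arm model, there would be 6.75/9 = 0.75 events per factor. The plan does not say whether they do.

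**Structure, by example.** Take a binary factor present in half the patients, with arm averages fixed at 20% and 5%.

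| Factor OR, placebo | Factor OR, statin | Statin OR, factor absent | Statin OR, factor present | Statin-only model shows |
|---|---|---|---|---|
| 3 | 3 | 0.20 | 0.20 | OR 3 |
| 3 | 1 | 0.40 | 0.13 | OR 1 |

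The first factor leaves the statin odds ratio unchanged but appears important. The second changes it threefold and appears irrelevant.

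**How often.** Simulation: 4,000 trials per setting, standard normal factor, marginal AIC 20% and 5%, likelihood-ratio tests at 0.05. The simulation standard error is at most √(0.25/4000) = 0.8 points.

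| Factor OR per SD | Statin-only test flags | Interaction test flags |
|---|---|---|
| 1 in both arms | 5.6% | 5.5% |
| 1.25 in both | 8.8% | 5.7% |
| 1.5 in both | 18.4% | 6.0% |
| 2 in both | 39.8% | 5.9% |
| 3 in both | 71.9% | 7.1% |
| 2 placebo, 1 statin | 6.0% | 31.5% |
| 3 placebo, 1 statin | 5.4% | 61.8% |

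**Scale.** The planned odds ratio is (0.05/0.95)/(0.20/0.80) = 0.2105. Applied to placebo risks of 10% and 30%, it gives 2.3% and 8.3% on statin, so absolute reductions of 7.7 and 21.7 points. Absolute benefit therefore varies with baseline risk even with no odds-ratio interaction.

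**Radiotherapy.** The SAP says: "Radiotherapy is not routinely used in the cohort and is used in <5% of cases". At 5%, that is about 7 patients per arm. With no radiotherapy effect, the chance of no AIC event among irradiated statin patients is (1 − 0.05 × 0.05)^135 = 71%. The chance of an empty cell in either arm is 79% (400,000 draws). At 3% use the figures are 82% and 90%.

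**Precision for LVEF.** Protocol 2.1, subsection b, gives 12-month LVEF SDs of 9 points (statin users) and 6 points (non-users) in a breast cancer cohort. The interaction standard error per SD of a factor is σ × √(2/135), or 0.73 at σ = 6 and 1.10 at σ = 9. The 95% half-widths are about 1.4 and 2.1 LVEF points.

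**The case against.** The core is hard to contest: no other section supplies a placebo comparison for the six remaining factors. The objections concern weight and detail.

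- **Secondary aim, low power.** The replacement has about 31% power for an odds ratio of 2 per SD on placebo against 1 on statin. For an evenly split binary factor with no main effect, the standard error of the interaction log odds ratio is √[2/(67.5 × 0.05 × 0.95) + 2/(67.5 × 0.20 × 0.80)] = 0.90, which gives 23% power for a ratio of odds ratios of 3. This stands. The change corrects what is estimated but will not often settle the question for AIC.
- **Scale.** A factor with a common odds ratio does alter absolute benefit, and the plan names no scale. This stands, so the first error applies on the odds-ratio scale. The missed modifier is the firmer argument.
- **Assumed strengths.** At an odds ratio of 1.25 the false-flag rate is only 9%; the 40% and 72% figures need strong factors. The simulated factor is continuous, while sex, cardiac history and radiotherapy are binary. Both limits stand, but the structural point depends on neither.
- **LVEF interval.** The SD of 9 rests on 8 statin users, and both SDs are unadjusted. Adjustment for baseline LVEF should, if anything, narrow the interval.
- **Multiplicity.** If independent, 8 interaction tests give at least one false flag with probability 1 − 0.95^8 = 34%, and 16 tests with probability 56%. This stands and supports an explicit exploratory label.
- **Already handled in part.** The dose interaction is the right kind of test, but it covers one factor of nine and is labelled post hoc.

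**Conclusion.** The concern holds. As written, the Aim 1a model answers a different question from the one posed. That follows from its structure and needs no assumed number. The frequency of each error does rest on the assumed factor strengths and on the planned 20% and 5% rates with 135 per arm. On the odds-ratio scale, false flags range from 9% to 72% for odds ratios of 1.25 to 3 per SD, and the true modifiers examined are detected only at chance. The aim should be corrected before analysis. The primary chi-square comparison is not affected.

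**What to change.** Replace the statin-only model in Aim 1a:

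- In all randomised patients, one factor at a time, fit treatment, factor and treatment × factor for AIC at 12 months. Firth-penalised logistic regression is a reasonable choice given about 34 expected events.
- Report the interaction odds ratio with its 95% CI and, because the answer depends on scale, the risk difference by factor level, at prespecified values for continuous factors.
- Fit the same terms in a linear model for 12-month LVEF, adjusted for baseline LVEF.
- Name the outcome and the scale, state the number of interaction tests, and label all results exploratory.
- For radiotherapy, report counts by arm only.
- State that received anthracycline dose is a post-randomisation variable, since "dose adjustments are made during therapy in response primarily to toxicities". The same applies to radiotherapy if given after randomisation; the documents do not say when. Treat both results as descriptive.

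The cost is SAP wording and a few lines of code, using data already collected in both arms. The downside is the low power for AIC, which the SAP should state. The LVEF model keeps the continuous information and is expected to be the more informative of the two.

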#### **Primary End-Point**

**Our primary endpoint will be the proportion of patients in each group that have a decrease of 10% or more in LVEF to <55% from baseline to 12 months after initiation of anthracyclines.**

**Assumptions:** We anticipate that 20% of the patients in the placebo group will reach the primary end-point. This assumption is based on significant prior literature; specifically, Limat *et al.* performed a prospective study where they enrolled patients similar to those proposed in this study (lymphoma receiving anthracycline-based chemotherapy) and performed a baseline measurement of LVEF and a measurement at 1 year. Their primary end-point was a more stringent cut-off than recommended by guidelines or being used in this study, a decrease of >15% in LVEF. They found that 20% of their population had a reduction of >15% in LVEF. Using CMR, two studies have tested the percentage of patients with a significant reduction in LVEF after anthracyclines. In a prospective observational study, Drafts and colleagues found

that 26% of patients decreased their LVEF to <50% and in a prospective randomized study, Bosch and colleagues found that up to 33% of patients decreased their LVEF to <55%. In the single small randomized study which also used 40 mg of atorvastatin with 20 subjects in each arm, there was no decrease in LVEF after anthracyclines among patients on statins. Our base case assumptions are as follows: 20% of the placebo group and 5% of the statin treatment group will meet the primary endpoint and we will be able to enroll 300 patients meeting all inclusion and exclusion criteria. From these, we anticipate a drop-out rate of approximately 10% due to a one year mortality of  $\approx$ 5% and atorvastatin related side-effects in 4% of patients. The remaining 270 patients will provide us with a 98% power to detect a 15% difference in the proportions of those achieving the primary end-point at a one-sided significance level of 0.05. Moreover, we will have a 70% power if the difference in the percentage reaching the primary end-point between groups falls as low as 10%.

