#### **Secondary End-Points Aim 1:**

**Aim 1a.** We will test whether cardiac risks factors (blood pressure, age, sex, glucose or cholesterol levels, prior history of cardiac disease, LVEF at baseline) or cancer specific risk factors (anthracycline dose, radiotherapy) are predictive of the effect of statins on LVEF.

***Analysis Plan:*** In patients treated with statins, we will use a logistic regression model to evaluate whether cardiac risks factors or cancer specific risk factors are predictive of the effect of statins on LVEF. Patients on statins and eligible for statins will be excluded. Therefore, cholesterol levels will be relatively homogenous and we will not pre-stratify our cohort based on cholesterol. Radiotherapy is not routinely used in the cohort and is used in <5% of cases, there we will also not pre-stratify based on the use of radiotherapy. However, we will use cholesterol values (as a continuous variable) and the use of radiotherapy (as a binary variable) to perform a post-hoc analysis. Additionally, all patients are intended to have the same dose of anthracyclines and dose adjustments are made during therapy in response primarily to toxicities. Therefore, we will additionally test the interaction between the dose of anthracyclines and the effect of statins as a post-hoc analysis.

**Aim 1b.** We will test whether statins reduce cardiac events.

***Adjudication plan:*** The occurrence of clinical adverse cardiac events will be adjudicated based on consensus opinion of a clinical adjudication committee containing three board-certified cardiologists blinded to experimental group (Drs. [name], [name] and [name]).

***Analysis Plan:*** All statistical analyses will be performed based on intent-to-treat. Fisher exact tests will be used to determine whether statins decrease the combined end-point of death or heart failure.

**Aim 1c.** We will test whether statins are safe.

**Analysis Plan:** Chi-square will be used to test for differences between the two treatment groups for categorical secondary endpoints.

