**Primary End-Point**

**Our primary endpoint will be the proportion of patients in each group that have a decrease of 10% or more in LVEF to <55% from baseline to 12 months after initiation of anthracyclines.**

*Assumptions for Sample Size Calculation:* We anticipated that 20% of the patients in the placebo group will reach the primary end-point. This assumption is based on significant prior literature; specifically, Limat *et al.* performed a prospective study where they enrolled patients similar to those proposed in this study (lymphoma receiving anthracycline-based chemotherapy) and performed a baseline measurement of LVEF and a measurement at 1 year. Their primary end-point was a more stringent cut-off than recommended by guidelines or being used in this study, a decrease of >15% in LVEF. They found that 20% of their population had a reduction of >15% in LVEF. Using CMR, two studies have tested the percentage of patients with a significant reduction in LVEF after anthracyclines. In a prospective observational study, Drafts and colleagues found that 26% of patients decreased their LVEF to <50% and in a prospective randomized study, Bosch and colleagues found that up to 33% of patients decreased their echocardiographically-derived LVEF to <55%. In the single small, randomized study which also used 40 mg of atorvastatin with 20 subjects in each arm, there was no decrease in LVEF after anthracyclines among patients on statins.

Our base case assumptions are as follows: 20% of the placebo group and 5% of the statin treatment group will meet the primary endpoint and we will be able to enroll 300 patients meeting all inclusion and exclusion criteria. From these, we anticipate a drop-out rate of approximately 10% due to a one-year mortality of  $\approx$ 5-6% and atorvastatin related side-effects

in 4-5% of patients. The remaining 270 patients will provide us with a > 90% power to detect a 15% difference in the proportions of those achieving the primary end-point at a two-sided significance level of 0.05. Moreover, we will have a 70% power if the difference in the percentage reaching the primary end-point between groups falls as low as 10%.

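### Aim 1a plans a logistic model in statin patients only, without naming its outcome; on the trial's assumptions it has about 7 events for nine factors and no comparator, so it cannot show who benefits

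*SAP*

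**What the plan says.** The aim is to learn whether patient factors predict how much statins affect LVEF. The cardiac factors are "blood pressure, age, sex, glucose or cholesterol levels, prior history of cardiac disease, LVEF at baseline"; the cancer factors are anthracycline dose and radiotherapy. That makes nine. The analysis plan, identical in the SAP and protocol 13.1, restricts the analysis to patients treated with statins and states "we will use a logistic regression model to evaluate whether cardiac risks factors or cancer specific risk factors are predictive".

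Three things are left open: which binary variable is modelled, whether factors enter together or singly, and whether any selection or penalisation applies. Cholesterol and radiotherapy are in the list but are also assigned to a post-hoc analysis. Of radiotherapy the plan says "Radiotherapy is not routinely used in the cohort and is used in <5% of cases". A treatment interaction is mentioned only for anthracycline dose, again post hoc.

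The event rates come from the SAP's primary end-point section: "20% of the placebo group and 5% of the statin treatment group will meet the primary endpoint".

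**The concern.** The question and the tool do not match. The question is about an effect of treatment on LVEF, a continuous measurement taken in both arms. The tool needs a binary outcome and is applied to one arm.

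AIC (a fall of at least 10 points to below 55%) is the only binary LVEF outcome defined, and protocol Aims 2b and 3b apply logistic regression to that same end-point, so it is the natural reading here. If statins work as hoped, AIC will be rare in exactly the group to be modelled. The AIC definition also contains baseline LVEF, one of the candidate factors.

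At stake is the trial's only planned look at who benefits. A risk factor for AIC among treated patients could be reported as a predictor of statin benefit, or a handful of events could produce odds ratios that nobody can interpret.

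**Working it through.** **Inputs.** 300 enrolled ("we will be able to enroll 300 patients meeting all inclusion and exclusion criteria"); about 10% drop-out; 1:1 allocation (protocol 1.0); event rates of 20% and 5%.

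**Plan's own figures.** 300 × 0.90 = 270, or 135 per arm. Power = Φ{[d − z√(2p̄(1−p̄)/n)] / √[(p₁(1−p₁)+p₂(1−p₂))/n]}, with d = 0.15, p̄ = 0.125, n = 135.
- SAP, "two-sided significance level of 0.05": (0.15 − 1.96 × 0.0403)/0.0392 = 1.81, giving 96.5%. This agrees with "The remaining 270 patients will provide us with a > 90% power to detect a 15% difference".
- Protocol, "one-sided significance level of 0.05": 98.4%, matching its 98%.

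The inputs are therefore read correctly. Neither document gives an event count or power for Aim 1a.

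**Expected events, statin arm.** 135 × 0.05 = 6.75; 95% binomial range 2 to 12.
- Nine factors: 6.75/9 = 0.75 per factor.
- Seven factors (cholesterol and radiotherapy left as post hoc): 6.75/7 = 0.96.
- If the statin rate were 10%: 13.5 events, 1.5 per factor.
- Both arms, still on AIC: 27 + 6.75 = 33.75 events. With nine main effects, arm and nine interactions (19 terms) that is 1.8 per term.

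**Joint fit.** 1,000 simulated statin arms of 135 with no true effects. Assumptions: six continuous factors, sex 50%, cardiac history 10%, radiotherapy 5%. Separation means that at least one odds ratio is infinite.

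| Model | AIC rate | Separated |
|---|---|---|
| Nine factors | 5% | about 85% |
| Nine factors | 10% | about 64% |
| Seven, without radiotherapy and cardiac history | 5% | about 7% |

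The failure comes mainly from the two rare binary factors.

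**One factor at a time.**
- Radiotherapy at 5%, the top of the stated range: expected events among users 135 × 0.05 × 0.05 = 0.34; chance of none (1 − 0.0025)^135 = 71%.
- Cardiac history at an assumed 10%: (1 − 0.005)^135 = 51%.
- Continuous factor, per SD: SE of the log odds ratio ≈ 1/√(135 × 0.05 × 0.95) = 0.395, so the 95% CI multiplies and divides the estimate by e^(1.96 × 0.395) ≈ 2.2. An estimated odds ratio of 2 would run from about 0.9 to 4.3. Simulated power for a true odds ratio of 2 per SD is about 36%.
- Evenly split binary factor: SE ≈ 0.395/0.5 = 0.79, a CI factor of about 4.7.

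**Baseline LVEF.** AIC requires a fall of at least 10 points and a final value below 55. From a baseline b above 65 the fall must exceed b − 55, so it grows point for point. Illustration, assuming a change of mean −2 and SD 6 that is independent of baseline (64 ± 5): AIC risk is 9.1% for baselines 60–65, 4.8% for 65–70 and 0.8% for 70–75. The gradient depends on the independence assumption. If patients with higher baselines also fall more, it can weaken or stop being monotone. With so few events, and change independent of baseline, the association reached p < 0.05 in only about 9% to 17% of simulated statin arms.

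**Precision of the alternative.** For a binary factor with prevalence q, the SE of the arm-by-factor term is σ√{2[1/(135q) + 1/(135(1−q))]}. Take σ = 6 to 9, the 12-month SDs in the in-house breast cancer cohort (protocol 2.1 b), used as an assumption and before any gain from baseline adjustment. The 95% CI half-widths in LVEF points are then:
- q = 50%: 2.9 to 4.3
- q = 10%: 4.8 to 7.2
- q = 5%: 6.6 to 9.9

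**The case against.** The strongest reply is that the text commits to less than the criticism assumes. It does not name AIC as the Aim 1a outcome, although the protocol does name the primary end-point for Aims 2b and 3b. It does not say that nine factors enter together. Cholesterol and radiotherapy are set aside as post hoc. Aim 1a is secondary and leaves the primary chi-square test untouched. AIC is also the trial's chosen end-point, so keeping secondary work on that scale is defensible.

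Most of this stands as a description, but it does not rescue the plan. AIC is an inference; if another outcome is meant, the text has to say so. Entering factors singly avoids most of the separation but leaves the imprecision shown above. Neither choice supplies a comparator.

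Two stronger readings are tempting and unsupported:
- **That the model cannot be fitted or read at all.** Single-factor, reduced or penalised models can usually be fitted. The 85% applies to a joint unpenalised fit, which the plan does not specify, and rests partly on the assumed 10% cardiac history.
- **That baseline LVEF would emerge as the leading predictor as an artefact.** The tie by definition is real, but with about 7 events it would often not reach significance. The documents do not give the relation between baseline and change, which sets its size.

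**Conclusion.** The point holds as a specification and feasibility problem in a secondary aim. The outcome and the mode of entry are unspecified. Under the natural reading there are about 7 events (2 to 12), or 0.75 per listed factor and 0.96 with cholesterol and radiotherapy removed. A joint unpenalised fit would usually fail, and simpler fits would be too imprecise to interpret. The tie between AIC and baseline LVEF above 65% muddies that one factor without preventing a fit.

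The lack of a comparator does not depend on event numbers: a statin-only model can describe who has AIC on statins, not who gains from them.

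The event count rests on the plan's 5% rate and 135 evaluable statin patients. The separation figure also rests on the assumed factor prevalences. The likely harm is an uninformative or misread exploratory result, with no effect on the primary conclusion. It should be corrected because the correction is cheap.

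**What to change.** In SAP Aim 1a and protocol 13.1 Aim 1a, replace the logistic model with a linear model, fitted to both arms, one factor at a time:

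12-month CMR LVEF = baseline LVEF + arm + factor + arm × factor

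Where the factor is baseline LVEF itself, the model reduces to baseline, arm and their product. Report each arm-by-factor coefficient with its 95% CI, labelled exploratory. Tabulate AIC counts by factor and arm descriptively, without tests. Treat all nine factors in the same way, so that cholesterol, radiotherapy and dose no longer appear both as listed factors and as post-hoc analyses.

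The cost is a few lines in each document. CMR at baseline and 12 months is already in the study calendar, and protocol 11.1 already describes the outcome measure as LVEF compared between groups.

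There are two drawbacks. The result is no longer on the AIC scale of the primary end-point. Interaction estimates also remain imprecise: about ±3 to ±4 LVEF points for an evenly split factor and much wider for radiotherapy, so the analysis can indicate large differences in benefit but not rule out moderate ones.
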